### 9.2.2 MicroRNA analysis:

1) Evaluate changes in miR signature in patients with steroid refractory cGVHD on combination therapy with IL-2 and ECP. Experimental Approach: Plasma samples (1 mL) will be collected at baseline (at enrollment) and at 12 weeks (completion of treatment) - from all patients enrolled on protocol. Samples will be stored at -70C freezer. Total RNAs will be extracted from batched samples using 400 $\mu$ L plasma by mirVana PARIS kit (Ambion) according to manufacturer's instructions. *Caenorhabditis elegans* miRNA (cel-miR-39) will be used as spiked in control. Plasma miRNAs will be quantified using SYBR green-based quantitative reverse-transcriptase polymerase chain reaction (qRT-PCR). To compare the plasma miR profiles of the two groups of patients, we will use qPCR-based high throughput miRNA array that contains primers specific for 345 well-characterized human miRNAs. Cel-miR-39 will be used for normalization to obtain relative miRNA expression. Statistical Analysis: Hierarchical clustering analysis will be performed using Cluster 3.0. The Mann-Whitney test will be used to compare differences in plasma miR expression between responders and non-responders. Receiver operative characteristic (ROC) curves and area under the ROC curve will be used to assess the sensitivity and specificity of miR biomarkers and logistic regression analysis will be used to develop a miRNA panel predictive of response to therapy. Based on the literature we will focus our analysis on up regulation of miR-146a and down regulation of miR-106b and miR-21.

2) Evaluate miR signature in patients with cGVHD versus matched post HCT controls without cGVHD. Experimental approach. 1 ml plasma sample will be extracted upon enrollment from (n=20) patients with severe steroid refractory cGVHD and a control group of patients without manifestations of cGVHD (n=20) who have similar HCT characteristics (obtained through the Protocol #09050. PI: [name]). Plasma samples will be batched and tested for differential miR expression as described in section above- to analyze differential miR expression pattern.

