3) Study miRNA expression in Tcon with or without Treg suppression: Experimental approach: Peripheral blood mononuclear cell (PBMC's) from all enrolled patients will be extracted from whole blood using Ficoll paque density gradient centrifugation (GE healthcare) at baseline. The PBMC's will then be flow sorted into 95% pure population of Tregs (CD4+CD25+CD127-) and Tcons (CD4+CD25+CD127-) using FACSaria cell sorter (BD Biosciences). Co-culture of Tregs and Tcons will be done in 96 well round bottom plates (Corning star, Cambridge, MA). Cells will be plated at

density of  $1 \times 10^5$ /cells/well in RPMI 1640 media (0.2mL/well) and incubated at 37C for 72 hours. Cultures will be stimulated by 1 $\mu$ gm/mL anti-CD3 antibody (BD PharMingen, San Diego, CA). miRNA expression of Treg suppressed and Treg unsuppressed Tcons will be investigated by miRCURY LNA™ microRNA Array (Exiqon, Vedbaek, Denmark). The intensity of signal will be calculated after background subtraction. The threshold value to screen up or down regulation of miRNAs will be a fold change  $\geq 2.0$  or  $\leq 0.5$ . Analysis Plan: The specific time trend for each cell subset, cytokine and miR will be assessed using linear mixed effects modeling. The overall fit of the model will be evaluated graphically by taking a scatter plot of data for each and applying an overlay of the line generated by the model. An evaluation of the regulation patterns over time will be assessed by examining the slope patterns. To assess the possible impact of changes in expression on T cells, functional regression modeling will be used. Similar modeling techniques will be used to assess the impact of clinical events on expression.

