### 13.1 Study Design, Sample Size, and Accrual Rate

This single center/single arm, phase II clinical trial is designed to evaluate the anti-cGVHD activity of extracorporeal photopheresis (ECP) when combined with low dose IL-2, in patients with steroid refractory cGVHD, as assessed by overall cGVHD response rate (CR+PR+SD). The primary endpoint overall response (CR+PR+SD) is based on the NIH cGVHD consensus criteria; calculated as the percent of evaluable patients that have confirmed CR/PR or SD

This study will implement a Simon, optimal, two-stage design to evaluate the anti-cGVHD activity of the ECP/IL-2 regimen. The trial is expected to enroll 24 patients e sample size is based on the desire to discriminate a promising response rate of 50% from a current response rate of 25%. The null hypothesis

that the true response rate is 25% will be tested against a one-sided alternative. In the first stage, 9 patients will be accrued. If there are 2 or fewer responses in these 9 patients, the study will be stopped. Otherwise, 15 additional patients will be accrued for a total of 24. The null hypothesis will be rejected if 10 or more responses are observed in 24 patients. This design yields a type I error rate of 0.05 and power of .80 when the true response rate is 50%. Currently, about 20-25 new patients are referred to ECP per year. We expect that 6 patients to be enrolled per year with the expected completion of accrual in 4 years.

**Evaluable for Response:** As part of the primary analysis, patients will be considered evaluable for response if they are eligible, have baseline disease assessments, and receive protocol treatment of any duration. All such patients will be evaluated for clinical response. Our primary outcome will be the clinical response rate measured in all patients who are enrolled and receive any amount of protocol therapy.

Patients who are consented for the study but withdraw for any reason (progression of GVHD, infectious complications, insurance denial etc) prior to initiation of protocol therapy will not be eligible for response evaluation.

**Evaluable for Toxicity:** Patients will be considered evaluable for toxicity if they receive any study drug.

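### The Treg-suppression miRNA experiment calls regulation from a 2-fold cut alone: its unit is not stated and the contrast is not tested across patients

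*Combined protocol and SAP*

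**What the plan says.** Section 9.2.2, part 3, takes mononuclear cells "from all enrolled patients will be extracted from whole blood using Ficoll paque density gradient centrifugation (GE healthcare) at baseline", sorts them into Tregs and Tcons, co-cultures them, and then "miRNA expression of Treg suppressed and Treg unsuppressed Tcons will be investigated by" a microRNA array. The decision rule is "The threshold value to screen up or down regulation of miRNAs will be a fold change" of 2.0 or more, or 0.5 or less. No unit, variance estimate, test, interval or multiplicity control is attached to it.

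The analysis paragraph that closes part 3 has three elements:
- "The specific time trend for each cell subset, cytokine and miR will be assessed using linear mixed effects modeling".
- Changes in regulation during follow-up are then judged from the fitted slopes.
- "To assess the possible impact of changes in expression on T cells, functional regression modeling will be used", and comparable models are planned for how clinical events affect expression.

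The only two-group miRNA test named is in part 1: "The Mann-Whitney test will be used to compare differences in plasma miR expression between responders and non-responders". Section 13.2 does not mention the correlative studies.

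**The concern.** Each patient supplies both culture conditions, so the experiment would yield up to 24 within-patient ratios per miRNA. That replication is what separates a reproducible change from noise, and the stated rule does not use it. Its only input is the size of a ratio. A 2-fold ratio in one noisy culture counts, while a 1.5-fold change seen in every patient does not.

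Nothing else in the plan fills the gap. Mixed models and slopes describe change over time, and a culture done once at baseline has no time trend. Functional regression asks how expression affects T cells, not whether suppressed and unsuppressed Tcons differ. The Mann-Whitney test is unpaired and belongs to plasma samples compared by response status.

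At stake is the list of miRNAs reported as regulated by Treg suppression. As written, it would carry no stated error rate, and its content would depend on how the analyst chose to apply the cut.

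**Working it through.** **Inputs from the documents.** The cut is |log2 fold change| ≥ 1 (9.2.2, part 3). The number of patients is 9 if the trial stops at stage 1; "Otherwise, 15 additional patients will be accrued for a total of 24" (13.1). The plasma array in 9.2.2, part 1, has 345 miRNAs. No count is given for the part 3 array, so 345 is borrowed.

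**Assumptions.** The within-patient log2 ratio is d = log2(suppressed) − log2(unsuppressed), taken as normal with SD s across patients. The documents give no s; 0.25 to 0.7 is the main range, with 1.0 as a check. Pairing is inferred, because both subsets are sorted from the same patient's cells. A false call means a flag when the average change is zero.

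**The plan's own figure.** Section 13.1 sets the number of patients: stop if 2 or fewer of 9 respond, reject if 10 or more of 24 respond. The exact probability is the sum over x = 3 to 9 of P(X₁ = x)·P(X₂ ≥ 10 − x), with X₁ ~ Bin(9, p) and X₂ ~ Bin(15, p). It gives 0.0485 at p = 0.25 and 0.805 at p = 0.50, so the stated 0.05 and 0.80 reproduce. No operating characteristic is stated for part 3.

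**Reading 1: cut applied per patient, no true change.** The false-call probability per miRNA is q = 2·(1 − Φ(1/s)), and the expected number per patient is 345·q.

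| s | q | 345·q |
|---|---|---|
| 0.25 | 0.00006 | 0.02 |
| 0.35 | 0.0043 | 1.5 |
| 0.5 | 0.0455 | 16 |
| 0.7 | 0.153 | 53 |

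**Reading 2: cut applied to the mean of 24.** The standard error is s/√24, which is 0.102 at s = 0.5 and 0.143 at s = 0.7.
- No true change: 2·(1 − Φ(1/SE)) is about 1e-22 at s = 0.5, 3e-12 at s = 0.7 and 1e-6 at s = 1.0. False calls are negligible.
- Consistent 1.5-fold change: log2(1.5) = 0.585, which is 0.415 below the cut. At s = 0.5, z = 0.415/0.102 = 4.07 and P(flag) is about 0.00002. At s = 0.7, z = 0.415/0.143 = 2.90 and P(flag) is about 0.002. At s = 1.0 it is about 0.02.

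**A paired test on the same data.** This was simulated with 345 miRNAs, a paired t-test and Benjamini-Hochberg control at 5%. The entries are the share of truly changed miRNAs detected.

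| n | True change | s | Number truly changed | Paired test | Cut on mean |
|---|---|---|---|---|---|
| 24 | 1.5-fold | 0.5 | 20 | 98% | <0.1% |
| 24 | 1.5-fold | 0.7 | 20 | 74% | 0.2–0.3% |
| 24 | 1.5-fold | 0.7 | 3 | about 48% | 0.2% |
| 24 | 1.5-fold | 1.0 | 3 to 20 | about 10–19% | 2% |
| 9 | 2-fold | 0.5 | 20 | 89% | 49% |
| 9 | 2-fold | 0.7 | 20 | 41% | 50% |
| 9 | 2-fold | 0.7 | 3 | about 15% | 50% |

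With Bonferroni at 0.05/345 instead, power for a 1.5-fold change at n = 24 and s = 0.5 is still 0.85. At n = 9 and s = 0.5 it is 0.05.

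**The case against.** **The cut is only a filter.** The plan's verb is *screen*, which suggests a first pass. This would answer the point if a second step were written for the contrast. None is, so the output of the screen is the result.

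**A 2-fold cut sets the smallest effect of interest.** On that view, missing 1.5-fold changes is intended. This partly stands: a preference for large effects is legitimate, and on the mean of 24 a true 2.5-fold change passes about 99% of the time at s = 0.5 or 0.7. But the plan gives no such rationale, and a size threshold does not replace a statement of uncertainty. For the same reason, the 50% pass rate at a true change of exactly 2-fold is no evidence against the rule. An effect sitting on a threshold passes half the time by construction.

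**A reader might infer that the list would be mostly false calls.** The documents do not support that. If 20 of 345 miRNAs truly change 2-fold and the cut is per patient, the expected true calls are 20 × 0.5 = 10 and the false calls 325·q. The false share is then 0.2%, 12%, 60% or 83% at s = 0.25, 0.35, 0.5 or 0.7. It exceeds half only at an assumed SD of about 0.5 or more. On the mean of 24 there are almost no false calls.

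**A reader might also infer that the experiment cannot answer its own question.** That does not follow from the threshold. The array data would exist and could be analysed by a paired test at any time.

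**The stakes are small.** This stands. Part 3 is baseline only, is not among the endpoints in 11.2, is not the primary immunologic endpoint in 9.1, and drives no trial decision.

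**Conclusion.** The concern holds as a gap in an exploratory analysis. The fold-change cut is the only rule for the suppressed-versus-unsuppressed contrast, its unit is not stated, and no analysis in the plan tests the contrast across patients. The two readings behave in opposite ways. Per patient, the expected false calls run from about 0.02 to 53 per patient as the SD goes from 0.25 to 0.7. On the mean of 24, false calls nearly vanish, but a consistent 1.5-fold change is flagged less than 1% of the time at SD 0.5 to 0.7.

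That the rule is incomplete follows from the text, with pairing inferred. The sizes rest on assumed SDs, a borrowed count of 345 miRNAs and, for the paired test, the assumed number of truly changed miRNAs. The advantage of the paired test is clear at 24 patients and moderate SD. At 9 patients or large SD it shrinks and can reverse.

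This is a low-cost improvement with no bearing on the primary endpoint. Separately, part 3 gives Tregs and Tcons the same sort phenotype (CD4+CD25+CD127-). That must be reconciled before the contrast can be interpreted, whatever analysis is used.

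**What to change.** In 9.2.2, part 3, before the arrays are analysed:
- Define the unit as the within-patient log2 ratio, suppressed minus unsuppressed, from the same patient's baseline culture.
- Call a miRNA regulated from a paired or moderated t-test, or a Wilcoxon signed-rank test, across all patients with a baseline co-culture, at 5% FDR.
- Report the mean fold change with its 95% confidence interval for every miRNA, whether or not it is called.
- Keep 2-fold and 0.5-fold only as a label for large effects.

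The cost is a short change to the analysis text and a few lines of code. No extra blood, cultures or arrays are needed. There are two downsides. Single-patient 2-fold changes that do not reproduce are no longer listed. If the trial stops at 9 patients or the SD is large, the FDR-controlled test has little power and can detect fewer 2-fold changes than a cut on the mean (about 41% against 50% at n = 9, SD 0.7, with 20 truly changed). Reporting effect sizes and intervals for all miRNAs keeps those changes visible.

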#### 9.2.3 Cytokine assays:

Serum separator tubes will be used (yellow top) will be used to collect samples (5 ml) on each visit. Samples will be allowed to clot for 30 minutes at room temperature before centrifugation for 15 minutes at 1000 x g. Serum will be removed aliquotted and stored samples at  $\leq -20$  °C for batched analysis as described below.

REG3 ELISA kits will be purchased from MBL International (Ab-Match Assembly Human PAP1 kit and Ab-Match Universal kit), and measurements will be performed according to the manufacturer's protocol. Samples (diluted 1:10) and standards will be run in duplicate, absorbance will be measured with a SpectraMax M2 (Molecular Devices), and results calculated with SoftMax Pro Version 5.4 (Molecular Devices). Elafin, IL2R, HGF, TNFR1, and IL-8 ELISAs will be performed in duplicate using the quantikine immunoassay (R&D Biosystems). The quantikine assay is a 3.5-4.5 hour solid phase ELISA designed to measure human cytokines (TNF- $\alpha$ , Elafin, IL2R, HGF, IL-2, IL-4, IL-6, IL-8, BAFF, IFN- $\gamma$  and CXCL-4) in cell culture supernates, serum, and plasma. It contains *E. coli*-derived recombinant human cytokine/protein and antibodies raised against these specific proteins. This assay employs the quantitative sandwich enzyme immunoassay technique. A monoclonal antibody specific for the pre-specified cytokine is pre-coated onto a microplate. Standards and samples are pipetted into the wells and any cytokine present is bound by the immobilized antibody. After washing away any unbound substances, an enzyme-linked polyclonal antibody specific for the cytokine is added to the wells. Following a wash to remove any unbound antibody-enzyme reagent, a substrate solution is added to the wells and color develops in proportion to the amount of TNF- $\alpha$  bound in the initial step. The color development is stopped and the intensity of the color is measured.

## 11.0 Endpoint Evaluation Criteria/Measurement of Effect

---

### 11.1 Primary Endpoint

The primary activity endpoint is cGVHD response, based on the 2014 cGVHD NIH Consensus criteria. Confirmation of CR/PR or SD assessed by NIH Consensus criteria.

#### 11.1.1 Response Definitions:

##### **Complete Response:**

*Organ response:* resolution of all reversible manifestations related to cGVHD in a specific organ.

*Overall response:* resolution of all reversible manifestations in each organ or site of cGVHD involvement. Depending on relevant organ system involvement, patients will undergo repeat detailed assessment of oral, cutaneous, musculoskeletal and pulmonary systems.

##### **Partial Response:**

*Organ response:* at least 50% improvement in the scale used to measure disease manifestations related to cGVHD (e.g. a 50% decrease in skin rash from 80% BSA to 40% BSA), with a minimum of 25% improvement in the full scale as opposed solely to a percentage of the starting value (Appendix F; Section 17.6)

##### **Overall Response:**

Improvement in measure at least one organ or site, without progression in measures at any other organ or site. The NIH global severity of chronic GVHD assessment criteria will be used to evaluate the response to therapeutic intervention in one or more involved organs. Of note, for global ratings and categorical scales, a 1-point change in a 3- or 7- point scale or a 2- to 3- change on a 0- to 10- point scale (0.5 SD change) would be considered clinically meaningful. Additionally, the hallmark for response to therapy for bronchiolitis obliterans syndrome (BOS) is stabilization of lung function with no further decrease in FEV1 during a 3-month period.

**Progressive Disease:** Organ progression: an absolute increase of at least 25% in the scale used to measure disease manifestations related to cGVHD. Of note, for global ratings and categorical scales, a 1-point change in a 3- or 7- point scale or a 2- to 3- change on a 0- to 10- point scale (0.5 SD change) would be considered clinically meaningful. Additionally, clinical worsening of cGVHD is not synonymous with progressive cGVHD per NIH criteria, as patients may experience worsening symptoms that do not meet objective NIH criteria for progression. If so, they still have the option of discontinuation of IL-2 and initiating additional immunosuppression for lack of IL-2 efficacy; at the judgment of the treatment physician.

### 11.2 Secondary Endpoints

##### **Toxicity:**

Toxicity will be graded according to the NCI-Common Terminology Criteria for Adverse Events version 4.03. Unacceptable toxicity will be defined as any toxicities that are at least possibly related to either ECP or IL-2 and occur during cycle 1 (within 10 days of initiation of therapy).

##### **Overall Survival:**

Defined as the time interval from date of first dose of study drug to date of death from any cause.

**Failure-free Survival:**

Defined as the time interval from date of first dose of study drug to first documented cGVHD progression (necessitating change of treatment), malignancy relapse or progression or death from any cause, whichever occurs first.

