Evaluation of patients with cGVHD using validated and standardized response criteria is lacking at the present time and this is a major drawback while evaluating response to therapy across clinical trials. Inamoto et al. recently described a new outcome measure, failure-free survival (FFS), to access response to second-line agents in patients with cGVHD. Failure events include non-relapse mortality, recurrent malignancy, and change in systemic therapy. FFS is a meaningful clinical metric that could be used as a shorter-term success end point for clinical trials. In their analysis of 312 patients with cGVHD who were on at least 0.5 mg/kg of prednisone equivalent and started on second-line immunosuppressive therapy, the 6 month FFS was 56%. The majority of failures were due to initiation of third line therapy (34%) indicating progression of cGVHD, 7 % were due to NRM and 3% due to disease relapse. Predictors of treatment failure were high-risk disease at HCT, lower GI involvement and high NIH global score at initiation of second-line therapy. FFS will be included as a secondary end point in our cohort.

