### **5.5 Criteria for Removal from Treatment**

- Subject withdraws consent
- Non-compliance
- Administrative reasons (insurance loss or no coverage of IL-2 or ECP by third party payors)
- Any Grade 4 non hematologic adverse event
- Life threatening anaphylactic reaction to IL-2
- Recurrent or non-resolving grade 3 toxic event
- Malignant relapse
- Clinical worsening of GVHD requiring the addition of a new immunosuppressive medication. A 50% increase in the corticosteroid dose will be considered evidence of worsening GVHD. Changes in other immunosuppressive medication doses to maintain a therapeutic level alone will not be criteria for removal from the trial.

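### Failure-free survival in 11.2 leaves out treatment switches made without documented cGVHD progression, although the measure adopted in 2.1.1 counts a change in systemic therapy as a failure

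*Combined protocol and SAP*

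**What the plan says.** Section 2.1.1 introduces FFS as a recently described outcome for second-line cGVHD treatment: "Failure events include non-relapse mortality, recurrent malignancy, and change in systemic therapy". It then states that "FFS will be included as a secondary end point in our cohort". For the cited cohort of 312 patients it gives a 6-month FFS of 56%. Most failures were "initiation of third line therapy (34%) indicating progression of cGVHD"; of the rest, "7 % were due to NRM and 3% due to disease relapse".

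Section 11.2 measures FFS from the first dose to "first documented cGVHD progression (necessitating change of treatment), malignancy relapse or progression or death from any cause, whichever occurs first".

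Progression is defined only in 11.1.1, as an absolute increase of at least 25% on the scale for an organ. The same paragraph warns that clinical worsening is a different thing, because "patients may experience worsening symptoms that do not meet objective NIH criteria for progression". Those patients may come off IL-2 and receive further immunosuppressive treatment for lack of effect, if the physician so judges. Section 5.5 lists "Clinical worsening of GVHD requiring the addition of a new immunosuppressive medication" among the reasons for removal from treatment, alongside several toxicity criteria.

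Section 1.2 asks for FFS to be estimated through 1 year. The analysis plan in 13.2 does not mention FFS.

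**The concern.** In 2.1.1 a change of systemic therapy is enough for failure. In 11.2 it is attached to documented progression, and no reason is given for the difference. The protocol itself describes the patients who fall between the two definitions: those who worsen, do not meet the progression criteria, and are switched because the regimen is not working. A patient removed for toxicity who then starts another agent is in the same position.

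At stake is what the reported FFS means. As worded, a patient whose treatment has been abandoned can still be counted as failure-free. Whether a switch is an event also depends on whether a progression threshold was scored and documented.

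**Working it through.** **1. Reproduce the cited figure.** Inputs from 2.1.1: failures at 6 months of 34% (third-line therapy), 7% (non-relapse mortality) and 3% (relapse).

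34 + 7 + 3 = 44, and 100 − 44 = 56%, as stated. Treatment change makes up 34/44 = 77% of the failures, so the component on which the definitions differ is the largest one.

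**2. Compare the events.**

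| Event | Measure in 2.1.1 | Definition in 11.2 |
|---|---|---|
| Death without relapse | failure | failure |
| Malignancy relapse | failure | failure |
| Switch with documented progression | failure | failure |
| Switch for worsening short of progression | failure | not listed |
| Switch after toxicity | failure, on the literal wording | not listed |

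If the words in parentheses in 11.2 are read as a condition, its events are a subset of those in 2.1.1. FFS under 11.2 is then at or above FFS under 2.1.1, apart from small timing differences when progression is documented before the switch. The direction is the same whether uncounted switchers are censored at the switch or simply followed on. The documents do not say which applies.

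**3. Possible size.** Let f be the fraction of treatment changes made without documented progression. The documents give no value, so f is an assumption ranging from 0 to 1. Applied to the cited cohort at 6 months:

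- Upper bound, if no uncounted switcher fails later: FFS(f) = 56 + 34f.
- Constant-hazard version, in which uncounted switchers stay at risk of the remaining events: FFS(f) = 0.56 raised to the power (44 − 34f)/44.

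| f | Upper bound | Constant hazard |
|---|---|---|
| 0 | 56.0% | 56.0% |
| 0.10 | 59.4% | 58.6% |
| 0.25 | 64.5% | 62.6% |
| 0.50 | 73.0% | 70.1% |
| 1 | 90.0% | 87.7% |

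For example, at f = 0.25 the exponent is (44 − 8.5)/44 = 0.807, and 0.56 to that power is 0.626.

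**4. Set this against precision.** With 24 patients, 56% is about 13 or 14 patients. The exact 95% intervals are 0.33 to 0.74 for 13/24 and 0.37 to 0.78 for 14/24. The upper-bound values at f = 0.25 and f = 0.5 lie inside both.

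**5. Check data capture.** Section 5.2.1 ends protocol-specific follow-up data after the initial 12 weeks, and 5.4 requires no research data collection during extended therapy. The calendar in Section 10 stops at week 16. Section 12.1.3 does list follow-up/survival forms, but no text says they record new cGVHD therapy. A switch after week 12 therefore has no stated route into the data, although the objective runs to 1 year.

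**The case against.** The strongest reply is that 11.2 does not name the NIH criteria. Section 2.1.1 itself describes third-line treatment as a sign of progression, so the authors may have meant any switch for worsening to count as progression. The Progressive Disease paragraph also calls smaller changes on global and categorical scales clinically meaningful; if those count, fewer switches fall short. This stands as far as it shows an ambiguity, and it argues for a small f. It does not remove the problem. The only definition of progression in the protocol is in 11.1.1, and that text rejects the equivalence for this trial. Even on the broad reading, switches after toxicity are still left out.

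Secondly, if the words in parentheses are only descriptive, progression without a switch would also be an event. That would push FFS down, so the upward direction depends on reading them as a condition.

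Thirdly, a reader might infer that the trial's FFS is biased upward against a 56% benchmark. The documents do not support that. The figure appears once, as background, and no test, threshold or decision uses it; 1.2 asks only for estimation. The settings also differ. The cited cohort was on at least 0.5 mg/kg of prednisone equivalent, was starting second-line therapy, and is reported at 6 months. This trial admits patients from 0.20 mg/kg/day (3.1.1), does not restrict prior lines (3.1.6), and reports through 1 year. Correcting the definition would not make the two figures comparable.

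Lastly, 2.1.1 speaks of a change in systemic therapy without adding that any reason counts, and third-line starts are the only kind it reports. That toxicity switches count in the published measure follows from the literal wording here and cannot be checked further from the documents.

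**Conclusion.** The mismatch is real and worth correcting. Taking progression as defined in 11.1.1 and the words in parentheses as a condition, patients switched for worsening short of progression, or after toxicity, have no FFS event at the switch. The estimate is then at or above FFS under the measure that 2.1.1 says is being adopted.

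The size cannot be fixed from the documents. In the cited cohort the shift at 6 months would be at most 34f points, with f assumed, and somewhat less under constant hazards. In a trial of 24 a small f would be hidden by imprecision.

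The consequence is limited to the meaning of a descriptive secondary endpoint. The primary endpoint, the sample size and its error rates, and the stopping rules do not use FFS.

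**What to change.** In 11.2, define FFS as the time from first dose to the first of:

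- start of a new systemic therapy for cGVHD, whether or not progression criteria are documented;
- malignancy relapse or progression;
- death from any cause.

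State whether a corticosteroid increase counts as an event, since 5.5 treats a 50% increase as evidence of worsening. If the present definition is wanted as well, keep it under a different name.

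Add the start date of any new systemic cGVHD therapy to the follow-up/survival forms in 12.1.3, collected through 1 year, and reconcile this with the end of data collection at 12 weeks in 5.2.1. Do not add a formal comparison with 56%.

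The cost is a short change to 11.2 and one extra follow-up item collected to 1 year. Reported FFS may be lower than under the present wording.
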